8.5. Changes From Protocol-Specified PK Analyses

There are no deviations from the protocol-specified PK analyses.

9. ANALYSIS ON PARTICIPANT-REPORTED OUTCOMES

Participant Reported Outcomes (PRO) will be analyzed based on the Full Analysis Set using all PRO data collected on-treatment (ie, data collected up to 1 day after the last dose date of B/F/TAF), which involve the following data:

- The HIV Treatment Satisfaction Questionnaire Status (HIVTSQs) are to be completed by participants at Day 1 (Baseline) and Weeks 12 and 24. The HIV Treatment Satisfaction Questionnaire Change (HIVTSQc) are to be completed by participants at Week 4.
- A study-specific questionnaire will be completed by participants on Day 1 and week 4 to document preference for oral vs injection therapy and specific reasons for decisions to switch from CAB+ RPV to oral therapy.

Any PRO data collected not on-treatment will be listed and flagged in the listings.

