## **6.5. Participant-Reported Outcomes: Questionnaires and Qualitative Interviews**

### **6.5.1.1. HIV Treatment Satisfaction Status (HIVTSQs)**

HIVTSQs are to be completed by the participant at Day 1 and Weeks 12 and 24 (see [Table 3](#)). Participant is to read questionnaire by himself/herself and write/mark answers directly onto questionnaires. See [Appendix 11.4.1](#) for questionnaire.

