**Table 2. Analysis Set Definitions**

Analysis Set	Description
All Enrolled Analysis Set	The All Enrolled Analysis Set includes all participants enrolled into the study after screening. This is the primary analysis set for listings.
Full Analysis Set	The primary analysis set for efficacy analyses is defined as Full Analysis Set (FAS), which will include all enrolled participants who have received at least 1 dose of study drug.
Safety Analysis Set	The primary analysis set for safety analyses, participant reported outcomes analysis is defined as the Safety Analysis Set, which will include all enrolled participants who have received at least 1 dose of study drug. All the data collected up to 30 days after participants permanently discontinue their study drug will be included in the safety and participant reported outcomes, unless specified otherwise.
PK Analysis Set	The primary analysis set for PK analyses is defined as the PK Analysis Set, which will include all enrolled participants who have received at least 1 dose of study drug, and have at least 1 non-missing PK concentration datum for any analyte of interest reported by the PK laboratory.

FAS = full analysis set; PK = pharmacokinetics

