Study Drug Accountability		X	X	X	X	X	X	
Study Drug Dispensation		X		X				
Observed Dosing		X	X	X				Participants must take their study drug in the clinic for observed dosing on Day 1, Week 4, and Week 12.

CBC = complete blood count; CD4+ = clusters of differentiation 4; DNA = deoxyribonucleic acid; DBS = dried blood spot; ESDD = early study drug discontinuation; GFR = glomerular filtration rate calculated using the Cockcroft-Gault equation; HBV = hepatitis B virus; HCV = hepatitis C virus; HIV-1 = human immunodeficiency virus type 1; HIVTSQs = HIV treatment satisfaction status questionnaire [quantitative]; HIVTSQc = HIV treatment satisfaction change questionnaire [quantitative]; RNA = Ribonucleic acid; PK = pharmacokinetic(s); TFV-DP = tenofovir diphosphate.

- a Evaluations to be completed within 42 days prior to Day 1 visit.
- b Participants will be dispensed study drug at the Day 1 visit; initiation of treatment with the study drug must take place in the clinic for observed dosing at Day 1 visit.
- c All study visits are to be scheduled relative to the Day 1 visit date. Visit windows are  $\pm 2$  days of the protocol-specified date through Week 12,  $\pm 6$  days of the protocol-specified date for Week 24. For the purpose of scheduling a 30-day follow-up visit, a  $\pm 6$ -day window may be used. Those participants who prematurely discontinue study drug and continue in the study through at least one subsequent visit after the early study drug discontinuation visit will not be required to complete the 30-day follow-up visit.
- d Only applies to participants who miss the Week 24 visit, and must be completed within 30 days of discontinuing study drug.
- e Early study drug discontinuation visit to occur within 72 hours of last dose of study drug.
- f Chemistry profile: alkaline phosphatase, AST, ALT, total bilirubin, direct and indirect bilirubin, total protein, albumin, bicarbonate, BUN, calcium, chloride, creatinine, glucose, potassium, and sodium.
- g For any post-Day -1 visit, if the HIV-1 RNA value is  $\geq 50$  copies/mL, a retest should be performed at a scheduled or unscheduled visit 2-4 weeks after the date of the original test.

- h Hepatitis B virus surface Antigen (HBsAg), Hepatitis B core antibody (HBcAb), and Hepatitis C virus (HCV) serologies (reflex HCV RNA is performed in participants with positive HCV Ab serology)

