6. EFFICACY ANALYSES

Efficacy data will be summarized for the participants in the FAS. For the FAS, all efficacy data, including data collected after the last dose of study drug, will be included, unless specified otherwise.

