6.3. Analysis of the Additional Efficacy Endpoints

6.3.1. Analysis of CD4 Cell Counts and CD4 Percentages

The change from baseline in CD4 cell counts and CD4 percentages will be summarized by visit for participants in the FAS based on observed, on-treatment data (ie, data collected up to 1 day after the last dose date of B/F/TAF) using descriptive statistics.

The mean and 95% CI of change from baseline in CD4 cell count over time will be plotted using observed data for the FAS.

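### The SAP summarises participant-reported outcomes only to last dose + 1 day where the protocol allows 30 days, without recording the change; the same cut drops some CD4 values from timely discontinuation visits

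*SAP*

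**What the plan says.** **Participant-reported outcomes (PROs).** Protocol Table 2 assigns PROs to the Safety Analysis Set. It states that data collected up to 30 days after permanent discontinuation "will be included in the safety and participant reported outcomes, unless specified otherwise". SAP Section 9 moves PROs to the Full Analysis Set and summarises them "using all PRO data collected on-treatment (ie, data collected up to 1 day after the last dose date of B/F/TAF". The remainder go to listings: "Any PRO data collected not on-treatment will be listed and flagged in the listings". SAP Section 3.1.3 keeps the 30-day sentence for safety only.

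**CD4.** SAP Section 6 sets a general rule that "all efficacy data, including data collected after the last dose of study drug, will be included, unless specified otherwise". Section 6.3.1 then limits CD4 to "observed, on-treatment data (ie, data collected up to 1 day after the last dose date of B/F/TAF". Protocol Section 8.5 states no on-treatment limit for CD4.

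**Schedule.** Protocol Section 6.5.1.1: "HIVTSQs are to be completed by the participant at Day 1 and Weeks 12 and 24". HIVTSQc is given at Week 4 only. In Protocol Table 3 the ESDD column includes CD4 but no questionnaire. Footnote e of that table reads: "Early study drug discontinuation visit to occur within 72 hours of last dose of study drug". Protocol Section 6.6.1 also allows the 72 hours to run from the participant's notice to the investigator, and Section 6.6.2 gives 30 days for an ESDD visit.

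**Endpoint rank.** HIVTSQc at Week 4 is the only satisfaction endpoint listed as secondary. SAP Section 9.1 classes HIVTSQs as an other endpoint.

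**The concern.** Protocol Section 8 says the SAP will give the details of the analyses, including any deviations from what was planned. SAP Sections 6, 7 and 8 each end with a subsection on changes from the protocol (6.4, 7.7 and 8.5). Section 9 has none, so the reduction from 30 days to 1 day is recorded nowhere.

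The protocol wants participants who stop B/F/TAF to stay in follow-up (Section 6.6), so their later questionnaires can exist. Under the SAP those forms move from the summaries to a flagged listing. Protocol Section 1.3 intends participant-reported data to help judge the net benefit of switching. In a single-arm study that judgement rests on within-person comparison with CAB+RPV. If the summaries keep only people still taking B/F/TAF, and those who stop are less satisfied, the reported means favour B/F/TAF.

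The CD4 issue is separate. The protocol schedules a CD4 draw at the ESDD visit, and the SAP then excludes some draws made on time.

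**Working it through.** The plan gives no figure to reproduce: Protocol Section 8.9 reports no sample size calculation, and neither document states an expected discontinuation rate or a satisfaction gap. The check is day arithmetic, followed by an illustration of size.

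**1. Which questionnaires count.** A form on study day v is summarised if v ≤ L + c, where L is the day of last dose, c = 1 in the SAP and c = 30 in Protocol Table 2. The earliest last-dose day that still counts is v − c, and not below day 1. Nominal days 28, 84 and 168 come from SAP Section 3.7.2. Brackets show the edges of the protocol visit windows: ±2 days through Week 12 and ±6 days at Week 24.

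| Form | v | Earliest L, c = 1 | Earliest L, c = 30 | Last-dose days lost at nominal v |
|---|---|---|---|---|
| HIVTSQc, Week 4 | 28 | 27 (25–29) | 1 | 1 to 26, all earlier stoppers who attend |
| HIVTSQs, Week 12 | 84 | 83 (81–85) | 54 (52–56) | 54 to 82 = 29 days |
| HIVTSQs, Week 24 | 168 | 167 (161–173) | 138 (132–144) | 138 to 166 = 29 days |

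People who stopped before about day 54 (for Week 12) or day 138 (for Week 24) are left out under either rule.

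**2. Effect of having no HIVTSQs at ESDD.** The first post-baseline HIVTSQs is at Week 12. With the 1-day cut, someone who stops before about day 83 has no summarised post-baseline HIVTSQs. If that person stopped on or after about day 27 and completed the Week 4 form, the HIVTSQc score still counts. Only those who stop before about day 27 have no summarised post-baseline satisfaction score at all.

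**3. CD4 at ESDD.** A visit within 72 hours of last dose falls 0, 1, 2 or 3 calendar days after it. Days 0 and 1 pass the cut and days 2 and 3 fail, so 2 of the 4 permitted calendar days yield a CD4 value that is not summarised. If the 30 days in Protocol Section 6.6.2 is meant, days 2 to 30 all fail.

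**4. Illustrative size.** If k of 35 participants are left out at a visit and the rest respond, the summarised mean exceeds the full mean by (k/35) × gap, where gap = mean of those kept − mean of those left out. Both k and the gap are assumptions.

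- k = 3, gap 10: 3/35 × 10 = 0.9 points
- k = 4, gap 10: 4/35 × 10 = 1.1 points
- k = 4, gap 20: 4/35 × 20 = 2.3 points
- k = 5, gap 20: 5/35 × 20 = 2.9 points

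The HIVTSQs total runs from 0 to 66 and the HIVTSQc total from −33 to 33, so both span 66 points. At Weeks 12 and 24 the change of window accounts for only part of such a shift, because the 30-day rule recovers only the 29-day band.

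**The case against.** The case for leaving the SAP alone has real substance.

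- **The exception is permitted.** Table 2 allows the SAP to specify otherwise, and Section 9 does so. For CD4 the 30-day sentence does not apply, since it covers safety and PROs, and SAP 6.3.1 is a written exception to the general efficacy rule.
- **An on-treatment summary is reasonable.** HIVTSQs asks about current treatment, so a score given after stopping may describe another regimen. Persistence is reported separately, reasons for stopping are listed, and the number of respondents appears with each score.

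Both stand, and both support keeping the on-treatment summary. Neither answers the lack of a stated reason for narrowing the PRO window, or the exclusion of CD4 values drawn on schedule.

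A reader might also infer more than the documents support:

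- *That early stoppers vanish from the satisfaction results.* They do not. Scores collected on treatment stay in, including Week 4 HIVTSQc for anyone who stops after that visit, and later forms are listed.
- *That the 72-hour visit window costs PRO data.* No questionnaire is scheduled at ESDD, so this mismatch touches CD4 only.
- *That the SAP denies changing the PRO analysis.* Its no-deviation statements cover efficacy, safety and PK; on PROs it is silent.
- *That the new analysis set changes who is included.* Both sets comprise enrolled participants with at least one dose.

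**Conclusion.** The point holds as one of disclosure and of a modest, avoidable loss of information on non-primary endpoints. The PRO window is reduced from 30 days to 1 day with no record or reason. That removes from the summaries every Week 4 attendee who stopped before about day 27, and a 29-day band of stoppers at each of Weeks 12 and 24. CD4 drawn 2 or 3 days after last dose at a timely ESDD visit is lost as well, and HIVTSQs is not collected at that visit.

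Upward bias should not be read as established. It requires stoppers to be less satisfied, and Protocol Section 3.3.1.1 lists reasons for stopping that need not imply this. The 0.9 to 2.9 points depend on the assumed 3 to 5 stoppers of 35 and a 10 to 20 point gap, with all of them absent at the visit in question. The co-primary safety endpoints keep their 30-day window and are unaffected.

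**What to change.** **SAP text (low cost; Section 1 says the SAP is finalised before the database):**

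1. State in Section 9 that the PRO window differs from Protocol Table 2, and give the reason.
2. Keep the on-treatment summary. Add a sensitivity summary of HIVTSQc and HIVTSQs using the protocol's 30-day window, and report the number excluded at each visit.
3. Set the on-treatment limit for CD4, and for any PRO collected at ESDD, at last dose + 3 days so that a visit within 72 hours of last dose counts. Note the CD4 limit in Section 6.4, since Protocol Section 8.5 has none.

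**Protocol schedule:**

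4. If data collection is still open, add HIVTSQs to the ESDD column. Tables 3-2 and 3-3 already assign study days 2 to 126 to Week 12 and days 127 to 210 to Week 24, so an ESDD value can be placed without carrying scores forward. The cost is one 12-item form for the few who stop, plus a schedule amendment with IRB approval (Protocol Section 9.2.1). A rule is also needed for two forms in one window: SAP Section 3.7.4 refers to Section 9.2 for this, but Section 9.2 covers only double answers to a single question. The SAP describes the interim analysis as already conducted, so this step may come too late; items 1 to 3 do not depend on it.
5. Reconcile Protocol Sections 6.6.1 and 6.6.2 and Table 3 footnote e on ESDD timing, and check that the limit in item 3 fits the result.

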9.1. Patient-Reported Outcomes

The PRO related secondary endpoint include:

- Change in HIV treatment satisfaction (HIVTSQc) score at Week 4.

The PRO related other endpoint include:

- Total score and change from baseline in HIVTSQs at Week 12 and 24.

The PRO related exploratory endpoints include:

- Week 12 reported experiences with CAB+RPV, reasons for switch to B/F/TAF, preferences for injectable and oral therapy from qualitative interviews of participant experience
- Participant-reported perceptions of CAB+RPV treatment, reasons for switch to B/F/TAF.

9.2. Analysis Methods

9.2.1. HIV Treatment Satisfaction Status (HIVTSQs) and HIV Treatment Satisfaction Change (HIVTSQc)

The HIVTSQ “status version” (**HIVTSQs**, see Appendix 3) measures participants satisfaction with their current treatment. Participants respond to the HIVTSQ items using a Likert scale ranging from 0 to 6, where 0 represents the least favourable option (“very dissatisfied”) and 6 represents the most favourable option (“very satisfied”). See Appendix 3 for study specific questionnaire. A treatment satisfaction scale total will be calculated as the sum of the responses to the first 11 items on the **HIVTSQs** form (range from 0 to 66), where higher scores indicate a greater level of satisfaction with their HIV-1 treatment. Item 12 (pain/discomfort) will be treated as an individual item score.

The HIVTSQ “change version” (**HIVTSQc**, see Appendix 3) was designed to assess the change in treatment satisfaction between a participant’s previous and current treatment. The individual items are scored from -3 (“much less satisfied now”) to 3 (“much more satisfied now”). A treatment satisfaction scale total in change will be calculated as the sum of the responses to the first 11 items on the **HIVTSQc** form (range from -33 to 33), where higher scores indicate a greater improvement in treatment satisfaction with the new treatment, and lower scores indicate lower treatment satisfaction with the new treatment, and a score of zero represents no change in satisfaction. Item 12 (pain/discomfort) will be treated as an individual item score (Reference 1).

If a question is scaled more than once, then the average will be used for in-between choices (eg, use 2.5 if 2 and 3 are answered for the same question). If the two answers are not consecutive, then the answer will be treated as missing value (eg, use “missing” if 2 and 5 are answered for the same question). Missing values will not be imputed.

The following tables will be provided using the Full Analysis Set:

- Individual measurement of HIVTSQs by visit while receiving study drug (B/F/TAF)
- Summary of HIVTSQs total score and change from baseline by visit while receiving study drug (B/F/TAF)
- Individual measurement of HIVTSQc at Week 4 while receiving study drug (B/F/TAF)
- Summary of HIVTSQc total score at Week 4 while receiving study drug (B/F/TAF).

The HIVTSQs scale totals at Day 1 (Baseline), Weeks 12 and 24, and the HIVTSQc scale totals at Week 4 will be summarized using descriptive statistics (sample size, mean, SD, median, Q1, Q3, minimum, and maximum). The number and percent of participants with responses to each question will be provided at each visit.

The following figures may be provided using the Full Analysis Set:

- Mean (\pm SD) HIVTSQs by visit while receiving study drug (B/F/TAF)
- Mean (95% CIs) HIVTSQs by visit while receiving study drug (B/F/TAF).

In addition, by-participant listings for the numerical responses in HIVTSQs and HIVTSQc will be provided by participant ID number and visits in chronological order using the All Enrolled Analysis Set.

9.2.2. Additional Study-Specific Questions

Proportion of participants with specific reasons for each question related to participant experience with CAB + RPV will be summarized at Baseline (Day 1, see Appendix 4) and Week 4 (see Appendix 5) using the Full Analysis Set in the following summary tables:

- Study-specific Questionnaire on Day 1: Questions Related to Participant Experience with CAB + RPV
- Study-specific Questionnaire on Week 4: Questions Related to Participant Experience after switching to oral B/F/TAF.

By-participant listings of qualitative interview responses will be provided by participant ID number (in ascending order) on Day 1 and Week 4 for the Study GS-US-380-6738 Additional Questions for Participant Questionnaire and Responses using the All Enrolled Analysis Set.

11. SOFTWARE

SAS® Software Version 9.4. SAS Institute Inc., Cary, NC, USA.

12. SAP REVISION

Revision Date (DD MMM YYYY)	Section	Summary of Revision	Reason for Revision

Appendix 1. Schedule of Assessments

Study Procedures	Screening ^a	Day 1 ^b	Week 4 ^c	Week 12 ^c	Week 24 ^c	30-Day Follow-up ^d	ESDD ^e	Notes
Informed Consent	X							
Medical History	X							
Concomitant Medications	X	X	X	X	X	X	X	At screening, concomitant medications taken within 30 days prior to screening will be recorded; at subsequent visits all medications since the last study visit will be recorded
Adverse Events	X	X	X	X	X	X	X	
Complete Physical Examination	X							Complete physical examination (urogenital/anorectal examinations will be performed at the discretion of the investigator)
Symptom-Directed Physical Examination		X	X	X	X	X		Symptom-directed physical examination at all post-screening time points.
Vital Signs and Weight	X	X	X	X	X	X	X	
Height	X							
Urinalysis	X	X	X	X	X	X	X	
Urine Pregnancy		X	X	X	X	X	X	For participants of childbearing potential only
Serum Pregnancy	X							For participants of childbearing potential only
Chemistry Profile ^f	X	X	X	X	X	X	X	
Hematology Profile	X	X	X	X	X	X	X	CBC with differential and platelet count
CD4+ Cell Count	X	X		X	X		X	
Plasma HIV-1 RNA ^g	X	X	X	X	X	X	X	
HBV and HCV Serologies ^h	X							
Estimated GFR	X	X		X	X		X	Estimated GFR according to the Cockcroft-Gault formula for creatinine clearance
Metabolic Assessments ⁱ		X		X	X			
Baseline PK, Sparse PK: trough and postdose PK sample ^j		X	X	X	X			

Study Procedures	Screening ^a	Day 1 ^b	Week 4 ^c	Week 12 ^c	Week 24 ^c	30-Day Follow-up ^d	ESDD ^e	Notes
Plasma Storage Sample ^k		X	X	X	X		X	
Whole Blood sample for potential HIV DNA genotyping		X						Whole blood sample for virology analysis
Plasma HIV-1 genotyping/phenotyping sample ^l			X	X	X		X	HIV-1 genotype/phenotype resistance testing for participants with unconfirmed virologic rebound with HIV-1 RNA value \geq 200 copies/mL
Dried Blood Spot (DBS) collection			X	X	X		X	TFV-DP from DBS will be run in retrospect for participants with confirmed viral failure
HIVTSQs		X		X	X			
HIVTSc Questionnaire			X					
Additional Quantitative Interview Questions		X	X					
Qualitative interview			X					Qualitative interview will explore in-depth experiences on CAB+RPV, reasons for switch B/F/TAF and satisfaction post switch. The visit window for the interview is from week 3 to week 9
Study Drug Accountability		X	X	X	X	X	X	
Study Drug Dispensation		X		X				
Observed Dosing		X	X	X				Participants must take their study drug in the clinic for observed dosing on Day 1, Week 4, Week 12, .

CBC = complete blood count; CD4+ = clusters of differentiation 4; DNA = deoxyribonucleic acid; DBS = dried blood spot; ESDD = early study drug discontinuation; GFR = glomerular filtration rate calculated using the Cockcroft-Gault equation; HBV = hepatitis B virus; HCV = hepatitis C virus; HIV-1 = human immunodeficiency virus type 1; HIVTSQs = HIV treatment satisfaction status questionnaire [quantitative]; HIVTSQc = HIV treatment satisfaction change questionnaire [quantitative]; RNA = Ribonucleic acid; PK = pharmacokinetic(s); TFV-DP = tenofovir diphosphate.

a Evaluations to be completed within 42 days prior to Day 1 visit.

b Participants will be dispensed study drug at the Day 1 visit; initiation of treatment with the study drug must take place in the clinic for observed dosing at Day 1 visit.

c All study visits are to be scheduled relative to the Day 1 visit date. Visit windows are \pm 2 days of the protocol-specified date through Week 12, \pm 6 days of the protocol-specified date for Week 24. For the purpose of scheduling a 30-day follow-up visit, a \pm 6-day window may be used. Those participants who prematurely discontinue study drug and continue in the study through at least one subsequent visit after the early study drug discontinuation visit will not be required to complete the 30-day follow-up visit.

d Only applies to participants who miss the Week 24 visit and must be completed within 30 days of discontinuing study drug.

e Early study drug discontinuation visit to occur within 72 hours of last dose of study drug.

f Chemistry profile: alkaline phosphatase, AST, ALT, total bilirubin, direct and indirect bilirubin, total protein, albumin, bicarbonate, BUN, calcium, chloride, creatinine, glucose, potassium, and sodium.

- g For any post-Day -1 visit, if the HIV-1 RNA value is ≥ 50 copies/mL, a retest should be performed at a scheduled or unscheduled visit 2-4 weeks after the date of the original test.
- h Hepatitis B virus surface Antigen (HBsAg), Hepatitis B core antibody (HBcAb), and Hepatitis C virus (HCV) serologies (reflex HCV RNA is performed in participants with positive HCV Ab serology)
- i Metabolic Assessments: Fasting lipid panel (total cholesterol, HDL, direct LDL, triglycerides). If the participant has not fasted prior to the visit, the visit may proceed, but the participant must return within 72 hours in a fasted state.
- j A single trough plasma PK sample approximately 23 to 24 hours after the previous dose and prior to dosing on Weeks 4, 12, and 24, and a single post-dose plasma PK sample at approximately 2 hours (relative to B/F/TAF dosing observed by the study staff) at Weeks 4, 12, and 24 will be collected.
- k Plasma storage sample for safety, PK, and/or virology (Day 1, Weeks 4-24, and ESDD).
- l 1. HIV-1 genotype/phenotype resistance testing (which includes protease, reverse transcriptase, and integrase testing) only conducted for participants with confirmed virologic failure with HIV-1 RNA value ≥ 50 copies/mL. Following virologic rebound, participants will be asked to return to the clinic (2-3 weeks later) prior to the next scheduled visit or at the next scheduled study visit, for an HIV-1 RNA and HIV-1 genotype and phenotype blood draw. Based on the results of this testing, participants should be managed according to the Virologic Rebound Schema. Participants with HIV-1 RNA ≥ 50 copies/mL at Week 12 and/or 24 will be asked to return for an unscheduled visit within the visit window for a retest. Participants with HIV-1 RNA ≥ 200 copies/mL at ESDD, last visit, or Week 12 or 24 will also have resistance testing conducted.

